5.5 Separate exploratory/translational objectives and endpoints

The exploratory outcomes are to investigate the main effect of the second-stage treatment for participants who did not respond to their initial treatments and to identify the best sequence of prophylaxis regimens that lead to the lowest UTI rate.

5.6 Process evaluation

We will carry out a mixed methods process evaluation guided by the new MRC Framework²⁶ for developing and evaluating complex interventions to:

- understand acceptability and a qualitative understanding of adherence to the intervention, and issues around implementation.
- explore participants' and HCPs/trial recruiter's views on the trial processes including a qualitative overview of local site adaptations and contextual factors influencing trial delivery, and views on trial materials and processes (e.g. recruitment, consent and retention).

6 Trial design and setting

The VESPER Trial is a pragmatic, three-arm, multi-site, open-label, patient-randomised superiority trial with internal pilot, qualitative and economic evaluations comparing two intravesical treatments for the prevention of rUTI in women both directly and to the current guideline-recommended standard of second line daily oral antibiotics, during a 6-month treatment and 6-months post-treatment follow-up period.

The two intravesical treatment arms are intravesical antibiotics – 80mg of Gentamicin diluted to 50ml using normal saline and intravesical GAG replacement compounds (a range of agents are permitted including: laluril, Cystistat, Gepan). The daily oral antibiotics arm will use guideline recommended antibiotics which will include, but not be limited to; Nitrofurantoin (50/100mg), Trimethoprim (100mg), Amoxicillin (250mg) or Cefalexin (125/250mg once a day)

We will randomise participants using a 1:3:3 ratio using the covariate-adaptive randomisation procedure following the Pocock and Simon's minimisation method with an 80% random element^{27, 28}. Allocations will be minimised by previous UTI frequency (<=4/year; >4/year) and menopausal status (pre; peri/post), both of which have strong prognostic value. We require 412 participants in total (62 in the oral comparator arm and 175 in both intravesical experimental arms) as we are primarily interested in comparisons of each intravesical prophylaxis against standard care and then a head-to-head comparison of intravesical prophylaxes.

We will use a Sequential Multiple Assignment Randomised Trial (SMART) design²⁹. This enables women to be re-randomised to a different prophylactic regime if they do not respond to their initially allocated prophylaxis. This will allow us to explore the optimal sequence of prophylaxis regimens. We will define relapse as at least two episodes of UTI occurring in the 6-month treatment period in line with currently accepted definitions of recurrent UTI. All women will have a fixed 12-month post randomisation trial period. If a participant is re-randomised to a different arm, their treatment will start back to time zero ie if a participant gets re-randomised at the end of their 6-months treatment period, they would be on the new treatment for a further 6-months.

Our target population are adult (\geq 16 years) women with a documented history of recurrent uncomplicated UTI, for whom second-line treatments would be considered e.g. at least three episodes of symptomatic antibiotic-treated urinary infection in the previous 12 months or two episodes of UTI

Canolfan

in the last 6 months despite the use of first line treatments such as intravaginal oestrogen, the oral urinary antiseptic methenamine Hippurate or first-line low dose oral antibiotics.

Whilst the main mode of data capture will be electronic, we will provide alternatives for participants either on paper or by telephone. Urine and optional perineal swab samples will be taken at baseline and at subsequent hospital visits during both treatment and follow-up periods (12 months in total). Participants will also be requested to submit further urine samples to the central laboratory when they suspect a UTI based on their symptoms. Participants will be provided with the central laboratory address together with all sample collection materials that are needed.

Central laboratories contact details:

[name]

Specialist Antimicrobial Chemotherapy Unit,

Public Health Wales,

University Hospital of Wales,

[name],

[name]

The trial is a UK multi-centre trial involving 20 secondary care NHS organisations.

6.1 Adherence data:

We will use quantitative data to explore adherence and to describe differences between different modes of intravesical administration (self vs clinician-delivered) and the timing of this decision in relation to randomisation and whether this is associated with differential response, switching, and outcomes. We will similarly describe the variability (and association with response/outcomes) in prophylaxis implementation more generally.

6.2 Internal pilot phase

We have included a planned internal pilot phase, with progression criteria during the first 8 months of recruitment (study months 8-15). We will review recruitment, including site and participant enrolment, completeness of primary outcome data and treatment adherence. Early qualitative

Canolfan

interviews with participants and HCPs will inform us about trial processes and acceptability. Our recruitment estimates for the pilot have accounted for the fact that the study population are those who have failed first line treatments, considered published reviews and recommendations^{30, 31} and acknowledged that recruitment rates are slower when centres initially open. We plan for all sites to be open within the first 8 months with a staggered opening rate. Pooled data of NIHR funded studies show internal pilots typically recruit 15% of their participants within 33% of the total recruiting time³⁰. Our progression criteria below are based on these estimates:

Progression criteria	Red	Amber	Green
% Threshold	<60%	61 - 99%	100%
Recruitment rate/site/month	<0.5	0.5-0.99	>1
Number of sites opened	<12	12-18	>18
Total number of participants recruited	37	38 - 61	62

During the 8-month internal pilot phase, we predict the average recruitment rate would be 1 participants/site/month, which accounts for slower recruitment as sites open. The remaining recruitment time after the internal pilot is completed (14 months) estimates a 25% increase in recruitment rate with an average of 1.25 participants/site/month. PI co-applicants and expressions of interest from our 20 sites indicate that they would feasibly recruit 1-2 patients per month. We anticipate opening 18 of our 20 sites by the end of the pilot period. We will review eligibility rates and reasons for exclusions to ensure we are being as inclusive as possible. Also included in the progression criteria is the proportion of participants providing primary outcome data. We would anticipate a completion rate of 90%, rates below this will prompt a review of the process of capturing primary outcome data. The progression criteria have been designed to allow for mitigating strategies to be discussed to allow for some adaptation to recruitment processes. We will constantly be assessing the criteria during the internal pilot phase. We will discuss the results with our Trial Steering Committee, before reporting to the NIHR HTA Programme, for permission to proceed.

6.3 Qualitative evaluation during the internal pilot phase

During the pilot phase we will carry out qualitative engagement via brief interviews with around 5-10 HCPs/research team members and 5-10 trial participants (with option to include carer/supporters) to explore:

- the factors that influence different treatment options for women with rUTI
- attitudes, skills and confidence in recruiting women from under-represented groups onto the trial
- the factors that affect decision to participate in trials
- the participants' experiences of participating in the trial (particularly for women from underrepresented groups)

Rapid qualitative analysis will be carried out initially to allow for rapid feedback to the team and for wider reporting. Depending on the results, this data may also be included in a more detailed thematic analysis later in the study.

6.4 Risk assessment

We have made an initial risk assessment of the potential hazards associated with this trial including those occurring and resulting in harm to the participants or researchers. The investigational medicinal products (IMP) to be used in the trial are all in current use in the UK NHS. From this we judge that from an IMP perspective there is low risk to trial participants. Risks associated with the design and methods of the trial including the clinical procedures specified in the protocol, participants' rights related to consent and protection of data and the reliability of trial results have also been assessed. The robust design of the study to mitigate and manage these risks has led to the decision, supported by the sponsor, to apply for 'Type A' status (low risk - notification only) from the Medicines and Healthcare products Regulatory Agency (MHRA) and allow for a risk-proportionate trial management and monitoring approach to the trial. A structured Safety Monitoring Plan will be made to assess risk management by all relevant parties including the sponsor, regulators, and regulatory and governance staff. This will be submitted to the MHRA along with the notification application.

A Trial Risk Assessment has been completed to identify the potential hazards associated with the trial and to assess the likelihood of those hazards occurring and resulting in harm. This risk assessment has been completed in accordance with the MRC/DH/MHRA Joint project guidance document 'Riskadapted approaches to the management of Clinical Trials of Investigational Medicinal Products' and includes:

- The known and potential risks and benefits to human subjects
- How high the risk is compared to normal standard practice
- How the risk will be minimised/managed

This trial has been categorised as a TYPE A where the level of risk is no higher than the risk of standard medical care. A copy of the trial risk assessment may be requested from the Trial Manager. The trial risk assessment is used to determine the intensity and focus of monitoring activity (see section 25.1).

7 Site and Investigator selection

This trial will be carried out at participating sites within the UK. All sites who are interested in participating in the trial will be required to complete a registration form to confirm that they have adequate resources and experience to conduct the trial.

Before any Site can begin recruitment a Principal Investigator at each site must be identified. The following documents must be in place and copies sent to the VESPER Trial email account (see contact details on page 4):

- Confirmation of Capacity and Capability (C&C) from R&D department following sharing of local information pack.
- > Favourable opinion of host care organisation/PI from Main Ethics committee
- > MHRA approval
- A signed Trial Agreement
- > Current Curriculum Vitae and GCP training certificate of the Principal Investigator (PI)
- Completed Site Delegation Log and Roles and Responsibilities document

- Full contact details for all host care organisation personnel involved, indicating preferred contact
- A copy of the most recent approved version of the Participant Information Sheet(s) and Consent Form(s) on host care organisation headed paper
- > A copy of the most recent approved GP letter on host care organisation headed paper
- A copy of the most recent Pregnancy Information Sheet(s) and Consent Form(s) on host care organisation headed paper
- Returned copy of the Self-Evident Correction Log signed by the PI (if applicable).
- Executed MTA

Upon receipt of all the above documents, the Trial Manager will send written confirmation to the Principal Investigator/lead Research Nurse detailing that the site is now ready to recruit participants into the trial. This 'Green light' letter/email must be filed in each site's Investigator Site File

Occasionally during the trial, amendments may be made to the trial documentation listed above. CTR will issue the site with the latest version of the documents as soon as they become available. It is the responsibility of the CTR to ensure that they obtain local R&D approval for the new documents.

Site initiations will be via TEAMS teleconferences.

VESPER will take place in 20 large UK urology/urogynaecology centres each receiving around 15-20 referrals per month of women with uncomplicated rUTI from primary care chiefly through the standard NHS pathways. These centres have well-defined existing clinical pathways in place for the treatment of such patients and will also have experience in treating refractory patients which is our target population. We would estimate that each centre would see 4-6 patients per month with refractory rUTI and would expect each centre to recruit 21 patients for the trial. Any discrepancy in recruitment rate between centres will be monitored and addressed. Recruitment will be carried out by research staff in each of the centres and will involve a clear explanation of the trial including the background, study protocol and aims. If recruitment is not to target in the early phase of the trial, we will identify any common issues and explore the possibility of opening additional centres. We have 5 "reserve" centres already in mind. The embedded qualitative work involving patients and clinicians will also help guide trial processes to maximise recruitment, through exploring barriers and facilitators to participant involvement.

8 Participant selection

In line with the pragmatic nature of this trial we have deliberately minimised the exclusion criteria. We are aware that intravesical treatments currently only apply to those women who are refractory to first-line treatments and as such represent only around 20% of all female patients with rUTI. We felt it necessary to exclude women with structural or functional urinary tract abnormalities as treatment for these patients is usually directed at correction of the underlying abnormality rather than an extended period of prophylaxis. Women who are planning pregnancy or breast feeding have been excluded as antibiotic options in this patient group are limited.

We will exclude patients who have contraindications to any of the three planned trial interventions. Within the oral antibiotic arm there are three possible agents that could be used, and we feel it is unlikely that patients would be sensitive or allergic to all three of those agents. Data from previous trials (ALTAR and ANTIC) have confirmed that no patients were prevented from trial entry due to oral antibiotic sensitivities. With regards to intravesical treatments (GAG replacement and intravesical antibiotics) these are not generally absorbed into the systemic circulation due to the urothelial barrier and therefore sensitivity to these agents is almost unseen. Some patients have in the past shown an inability to retain intravesical treatments due to concomitant issues with continence, but we can usually give advice which enables sufficient retention. For example, we sometimes ask the patients to instil the treatment into the bladder at nighttime prior to going to sleep. For participants who are unable to self-catheterise at home, a clinic appointment will be offered to them to carry out the instillations and to encourage them to retain the instilled substance (Gentamicin or GAG) for as long as they can.

Participants are eligible for the trial if they meet all of the following inclusion criteria and none of the exclusion criteria apply:

8.1 Inclusion criteria

• Women (assigned female at birth) with recurrent uncomplicated UTI who have failed first-line treatments (at least three episodes of symptomatic antibiotic-treated urinary infection in the previous

12 months or two episodes of UTI in the last 6 months despite the use of first line treatments). Failed first-line treatments can include antibiotics, methenamine (antiseptic) or vaginal oestrogen.

VESPER

- Women aged >16 years
- Women able to receive intravesical treatments and take second-line oral antibiotic prophylaxis
- Women able to give informed consent
- Women willing to adhere to a 12-month study protocol

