3.1 See *Figure 1* for trial schema and participant flow diagram

Canolfan

Figure 1: trial schema and participant flow diagram

3.2 Trial lay summary.

Most women experience urine infections during their lifetime, but some get repeated episodes, which considerably reduce quality of life. This is known as recurrent urinary tract infection (rUTI) and is defined as at least two episodes in six months or three in a year. rUTI affects around 600,000 United Kingdom (UK) women and is a very common reason for antibiotic prescription. Overuse and misuse of antibiotics drives increased antimicrobial resistance, which is a critical global health threat. Daily, low-dose, oral antibiotics for up to 6 months is the standard preventative treatment for rUTI however they do not work for some women (about 20%). Patients with infections that are difficult to control may need treatment given directly into the bladder through the urethra (water pipe) using a very thin disposable single use catheter (known as bladder instillations). Patients usually have a series of these treatments over 6-months. Currently, about 75% of surveyed urology specialists report regular use of instillations but the supporting evidence for these treatments is lacking, and current clinical guidelines can only recommend more (second line) daily oral antibiotics.

The VESPER trial compares two treatments given directly into the bladder to prevent UTI against the current recommended treatment of daily oral second-line antibiotics. For this trial, women seen in a hospital urology/urogynaecology clinic with rUTI who have not improved after first-line treatments will be invited to participate. Failed first-line treatments can include antibiotics, methenamine (antiseptic) or vaginal oestrogen. The treatment given to each participant will be decided randomly and will be one of:

1. Gentamicin, an antibiotic, given into the bladder periodically over 6-months (see schedule).

2. Glycosaminoglycan (GAG) replacement preparations given into the bladder periodically over 6 months (see schedule) – these treatments reinforce the inner lining of the bladder and stop bacteria from sticking there.

3. Daily low-dose, second-line antibiotic treatment for 6 months. A range of NICE recommended antibiotics will be permitted, and the antibiotic choice will depend on the type of bacteria causing UTIs and patient tolerance to antibiotics (Standard Care).

Canolfan

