Recurrent urinary tract infections (rUTI) affect 2 - 6% of women, equating to at least 600,000 UK women based on current population figures. The vast majority (>90%) are classified as uncomplicated meaning there are no underlying structural or functional urinary tract abnormalities ¹². A recent study involving female rUTI patients revealed that they experience around seven UTI episodes/year ³. Guidelines recommend first-line preventative treatment with long-term (usually 3-6 months), lowdose, daily antibiotics ⁴⁻⁷ but these fail in around 1 in 5 women (equating to over 100,000 women in the UK per year)⁸. NICE currently only recommend second-line daily, low-dose oral antibiotics in these refractory cases, but this guidance is not based on robust evidence of efficacy ⁴. Due to this evidence gap, other national/international guidelines are unable to make any recommendations for this refractory patient group. Many clinicians use alternative strategies for refractory rUTI prevention including direct intravesical treatments. The two most commonly used intravesical treatments are antibiotics (gentamicin) or glycosaminoglycan (GAG) replacement compounds and both require patients to be temporarily catheterised for the administration of these treatments. A 2022 meta-

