15.3 Sample size

We aim to recruit 412 participants over 21 months and follow them up for a fixed 12-month period (62 in the oral comparator arm and 175 in both intravesical experimental arms). We are primarily interested in comparisons of each intravesical prophylaxis against standard care and then a head-to-head comparison of intravesical prophylaxes.

Two sets of comparisons are powered. The first set compares each intravesical prophylaxis arm to the second-line prophylactic oral antibiotics arm to detect a difference in the UTI rate of 1 (assumed UTI rate of 2 from previous studies³). This is calculated based on 90% power, and two-sided alpha of 0.05 (no multiplicity adjustment as comparisons is considered independent). This comparison requires 62 participants in each arm (1:1:1 ratio). The second set is to detect a difference in the UTI rate between the intravesical arms. This is calculated based on 90% power, 5% two-sided alpha (no adjustment as we are making this comparison as part of a fixed sequence. That is, we will only compare the intravesical prophylaxis arms head-to-head if both are superior to the second-line prophylactic oral antibiotics arm), with target effect size of 30% (i.e. a relative difference of 30% between intravesical arms, with an assumed UTI rate of one in one of the intravesical arms). This comparison requires 175 in each intravesical arms and hence 1:3:3 ratio.

Target differences between oral and intravesical treatments are based on PPI work. In line with previous studies³ the PPI group for VESPER overwhelmingly stated that any intravesical treatment demonstrating a reduction in UTI frequency of 1 episode per year greater than oral antibiotic tablets would be considered superior. Target differences between intravesical treatments are based on our clinician survey administered via UKCS which revealed that the majority of clinicians felt that for one intravesical treatment to be considered superior to another there would need to be a 30% or greater difference in efficacy. This sample size is further inflated to account for a 15% drop-out (as observed in the ALTAR trial³).

Although we are proposing a SMART design, our primary interest is the marginal effect of the initial prophylaxis, the comparison of each treatment sequence is considered exploratory and hence the SMART design has no impact on our required sample size.

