16.1 Main analysis

Descriptive statistics will be summarised using frequencies and percentages, means and standard deviations, or medians and interquartile ranges as appropriate. Recruitment, retention, and other trial processes (e.g. adherence to allocation) will be reported both overall, by arm, and disaggregated by site, menopausal status, previous UTI frequency, and previous type of failed treatment.

The primary analysis will be an intention to treat, including all randomised participants regardless of adherence or discontinuation of the initial treatment allocation or initiation of the subsequent treatment.

For the clinical-effectiveness primary outcome (rate of symptomatic, antibiotic-treated UTI, selfreported by participants from randomisation to the 6-month treatment period (verified from medical

Canolfan

records)), a Poisson/negative binomial regression model will be fitted to estimate incidence rate ratios, including fixed effects for allocation, covariate factors used in randomisation (prior frequency of UTI and menopausal status) and random effects to model heterogeneity between sites. Regression analysis results will be presented as point estimates with confidence intervals and p-values. The primary estimand for VESPER is below:

Primary clinical question: In women who fail first-line preventative treatment for rUTI, does the strategy to initially prescribe intravesical treatments result in a greater reduction in the rate of symptomatic UTIs over the subsequent 6 months compared to the current guideline-recommended second-line prophylactic antibiotic therapy?

The estimand is described by the following attributes:

- Population: women aged >16years with recurrent uncomplicated UTI who have failed firstline treatments requiring second-line prophylactic treatment and able to receive intravesical treatments and take second-line oral antibiotic prophylaxis.
- **Endpoint**: rate of symptomatic UTIs from randomisation to 6-months. •
- **Treatment condition**: The intravesical treatments and second-line oral antibiotic prophylaxis, regardless of adherence or discontinuation of the initial treatment allocation or initiation of the subsequent treatment (via re-randomisation) (treatment policy strategy);
- Remaining intercurrent events: Treatment adherence or discontinuation or initiation of the subsequent treatment are covered by previous attribute.

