16.1.1 Sub-group & interim analysis

To explore the extent to which there may be a differential intervention effects by the primary outcome, rate of symptomatic UTIs from randomisation to 6-months, the model fitted for the primary analysis will be extended by including a main and treatment group interaction term for menopausal status, previous UTI frequency, and type of failed first-line treatment. For the exploration of differential intervention effects by site, the primary analysis will be extended by allowing for different slopes across sites and compare this to the original model (random intercepts only) using the Likelihood-ratio test. Estimates from the statistical models (main effects and interaction terms) will be presented alongside 95% confidence intervals and p-values.

No formal interim analysis will be conducted.

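### The control is justified for women in whom antibiotic prophylaxis failed, but women who failed only methenamine or vaginal oestrogen also qualify, and the primary analysis pools the two groups without adjustment

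*Protocol*

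**What the plan says.** **Rationale.** Section 4 (Background) describes first-line prevention as long-term, low-dose daily antibiotics, "but these fail in around 1 in 5 women". It continues: "NICE currently only recommend second-line daily, low-dose oral antibiotics in these refractory cases". The lay summary (3.2) gives the same failure figure, about 20%, and says that guidelines can then offer only more daily antibiotics. Section 8 puts the target population at around 20% of women with recurrent UTI, the same share.

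**Eligibility.** Section 8.1 states: "Failed first-line treatments can include antibiotics, methenamine (antiseptic) or vaginal oestrogen". The lay summary agrees. Section 6 lists intravaginal oestrogen together with the "urinary antiseptic methenamine Hippurate or first-line low dose oral antibiotics", as alternatives. No criterion in 8.1 or 8.2 requires earlier antibiotic prophylaxis.

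**Design and analysis.** Sections 9.6.2 and 15.1 minimise on prior UTI frequency and menopausal status only. The primary model in 16.1 adjusts for "covariate factors used in randomisation (prior frequency of UTI and menopausal status") with random site effects. Section 16.1 also reports recruitment, retention and other trial processes by type of failed treatment. Section 16.1.1 extends the primary model with an "interaction term for menopausal status, previous UTI frequency, and type of failed first-line treatment". Section 15.3 sizes the oral comparison "to detect a difference in the UTI rate of 1 (assumed UTI rate of 2 from previous studies"), with 62 oral and 175 women in each intravesical arm.

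**The concern.** The rationale and the entry criteria describe different women. In a woman who has already failed daily antibiotics, the oral arm tests whether another antibiotic does better. In a woman who failed only methenamine or oestrogen, it may be her first antibiotic prophylaxis, which is a different comparator situation.

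The primary rate ratio averages over both. If the effect differs between them, a pooled null could obscure a benefit in antibiotic-refractory women. A pooled positive result could equally be quoted for antibiotic-refractory women although part of the evidence came from others. The trial is meant to inform guidelines, so readers will ask to which group the result applies. The protocol treats the factor as a possible effect modifier in 16.1.1, but neither balances nor adjusts for it, and the oral arm has only 62 women.

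**Working it through.** **1. The passages side by side**

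| Place | Who is meant |
|---|---|
| 4 Background; 3.2 lay summary (rationale) | women in whom daily antibiotics failed, about 1 in 5 |
| 3.2 lay summary (entry), 6, 8.1 | women who failed antibiotics, methenamine or vaginal oestrogen |
| 16.1 estimand population | women who failed first-line treatments, type not specified |
| 9.6.2, 15.1 minimisation | type of failed treatment not used |
| 16.1 primary model | type of failed treatment not used |
| 16.1.1 | type of failed treatment as an interaction |

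The mismatch between the first two rows needs no numerical assumption.

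**2. Does mixed eligibility by itself cost power?**

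Inputs from 15.3: control rate 2, intravesical rate 1, 62 v 175 women, two-sided 5%. The rates are read as events in the 6-month primary window, before the 15% drop-out allowance. Assumptions not in the protocol: half the women have no prior antibiotic prophylaxis (f = 0.5), and failing in 1 in 5 means at least two UTIs in 6 months under a Poisson count. Solving 1 − P(X ≤ 1) = 0.20 gives 0.824 events for these women on control.

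- Pooled control rate: 0.5 × 2 + 0.5 × 0.824 = 1.412.
- Variance of the log rate ratio: V = (1/r0 + k)/62 + (1/r1 + k)/175, where k is the over-dispersion.
- Power: Φ(|ln(r1/r0)|/√V − 1.96).

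| Scenario | r0, r1 | k = 0 | k = 0.5 |
|---|---|---|---|
| No such women | 2, 1 | over 99.9% | 99.3% |
| Half, common rate ratio 0.5 | 1.412, 0.706 | 99.9% | 97.8% |
| Half, intravesical rate held at 1 | 1.412, 1 | 75% | 54% |

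For the second row at k = 0.5, V = (0.708 + 0.5)/62 + (1.416 + 0.5)/175 = 0.0304 and √V = 0.1745. Power is Φ(0.693/0.1745 − 1.96) = Φ(2.01) = 97.8%.

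The third row puts intravesical treatment at 1 against 0.824 on oral antibiotics in the same women, a ratio of 1/0.824 = 1.21. The fall to 54–75% comes almost entirely from that assumed reversal of effect, not from the mixed eligibility.

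**3. What would adjustment gain?**

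Negative binomial simulation: 62 v 175, half the women without prior antibiotic prophylaxis, k = 0.5, common rate ratio, 600 runs per setting. Power without and then with the extra covariate:

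| Control rate in these women | Rate ratio 0.6 | Rate ratio 0.7 |
|---|---|---|
| 0.824 | 78% to 81% | 45% to 51% |
| 1.4 | 87% to 88% | 55% to 56% |
| 2.0 (not prognostic) | 91% to 91% | 62% to 62% |

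The gain is from none to about 6 points, depending on how prognostic the factor is.

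**4. How precise is an estimate by subgroup?**

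With an equal split there are 31 v 87.5 women per subgroup. At rates 2 v 1 and k = 0.5, V = 1.0/31 + 1.5/87.5 = 0.0494 and √V = 0.222. The 95% interval is the estimate multiplied and divided by exp(1.96 × 0.222) = 1.55. For the whole comparison V = 1.0/62 + 1.5/175 = 0.0247, √V = 0.157, and the factor is 1.36. With k = 0 the factors are 1.38 and 1.26.

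**The case against.** The strongest reply is that the estimand in 16.1 already matches the enrolled women. It concerns failure of first-line treatments, section 6 defines the target population with all three, and second-line can mean the next line of prophylaxis rather than a second antibiotic. The breadth is deliberate in a pragmatic trial, and the interaction by type of failed treatment is prespecified. Leaving a covariate out does not bias a randomised comparison, and the protocol credits strong prognostic value only to the two minimisation factors.

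Much of this stands. On that reading the label is consistent and the pooled estimand is legitimate. But the 1-in-5 rationale and the guideline statement about refractory cases then no longer describe everyone enrolled, so the passages still need reconciling. A planned interaction also does not say which estimate supports a statement about antibiotic-refractory women.

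A reader might go further and infer that the trial is underpowered, with power of 54–75% at a half share. The documents do not support this: the share and the control rate are not stated, and the figures need the effect to reverse. Holding the intravesical rate fixed but reading the rates as annual (1.0 v 0.5 per 6 months), the fall is 5 points with Poisson counts (98.7% to 94.1%) or 9 points with over-dispersion 0.5. A reader might also infer that the control works in about 80% of these women. That is only the complement of a failure figure for women given first-line antibiotics in general, not for women already recurring on methenamine or oestrogen.

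**Conclusion.** The point holds as one of interpretation and adjustment. The rationale rests on failure of antibiotic prophylaxis, entry does not require it, and the primary rate ratio pools the two situations with the distinguishing factor outside both minimisation and the primary model. This follows from the text alone.

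Its size cannot be stated, because the protocol gives neither the share of women without prior antibiotic prophylaxis nor their UTI rate on control. No loss of power is demonstrated, and no figure in 15.3 is shown to be wrong on this account. The gain from adjustment is 0 to about 6 points under the simulated assumptions. The more useful gain is clarity: the pooled result applies to women who failed any listed first-line treatment, while a conclusion about antibiotic-refractory women needs its own, less precise estimate.

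**What to change.** 1. In 16.1, add prior failure of antibiotic prophylaxis (yes/no) as a fixed effect in the primary model. It can be derived from the type of failed treatment already recorded for 16.1.1.
2. From the interaction model in 16.1.1, report the treatment effect in women with and without that failure beside the primary result, with confidence intervals and a note on the low precision with 62 controls. Base any conclusion about antibiotic-refractory women on that estimate, and state that the pooled result applies to women who failed any listed first-line treatment.
3. Reconcile the wording of section 4 and the lay summary with 8.1, so that the rationale describes the women who can enter.

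The cost is protocol and SAP wording and one derived covariate, settled before database lock. No extra participants or data are needed, and eligibility, treatment and section 15.3 can stay as they are on this point.
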